Refining the Shared Decision Making Process Survey in ADHD Medication Decisions

Protocol and analysis plan

PI: [name]

Statistician: [name]

Clinical Trials.gov: NCT05048186

IRB at Mass General Brigham: # 2019P001434

Funding: R01HS025718 from the Agency for Healthcare Research and Quality (AHRQ)

Co-Investigators and Study team: [name] (Massachusetts General Hospital (MGH), Harvard Medical School (HMS)), [name] (Center for Survey Research, University of Massachusetts Boston), [name] (Cincinnati Children's Hospital), [name] (MGH), [name] (MGH, HMS), [name] (MGH)

Website: www.mghdecisionsciences.org

Contact: [name] [contact]

Document Date: August 10, 2023

Background: Shared decision making (SDM) is recommended for common pediatric conditions; however, there is limited data on measures of SDM in pediatrics. This study adapted the SDM Process scale and examined validity and reliability of the scale for ADHD treatment decisions.

Purpose: The primary purpose is to examine the performance of the SDM Process scale for pediatric medical decisions. A secondary purpose is to evaluate the impact of a Decision Aid on participant knowledge of ADHD treatment options.

Design: Retrospective observation study of parents who had recently made a decision about medication for their child's ADHD. We worked with a national sampling firm to obtain a target of 500 responses. The sampling firm sent an email invitation to potentially eligible panel members informing them that a survey is available for which they are eligible. Respondents choose to participate or not. The sampling firm's database does not hold sensitive or confidential panelist information. The firm stopped emailing web panel members once they received 500 completed surveys. The study investigators received de-identified participant information from the firm and did not have access to participants' emails or any of their personal information.

After completing the main decision making surveys, participants in the sample will be randomized 1:1 to one of two arms. Participants in the intervention arm will review a Decision Aid (patient educational tool) partway through the survey and those in the control arm will not receive any educational materials.

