Sample: Participants were caregivers (n=498) of children (aged 5-13) diagnosed with ADHD, who had made a decision about ADHD medication in the last 2 years. The sample was not a national probability sample; however, the recruitment efforts were managed to be geographically diverse and to have at least 25% non-White respondents.

Intervention: Intervention arm received the Behavioral Attention Deficit Hyperactivity Disorder Treatment Decision Aid presenting benefits and harms of different treatments for ADHD. The decision aid was created at Cincinnati Children's Hospital.

The control arm did not receive any materials.

Survey protocol: The online survey was fielded between February 2021 and March 2021. Participants completed screener questions to determine eligibility. Then, they reviewed an information sheet that described the study and had to acknowledge that they read it and were willing to continue to the survey. Then, they continued to the survey. They were asked to identify the main decision they made about ADHD medicine over the past two years (“In the last 2 years, what was the main decision you made about using medicine to treat your child’s ADHD?”; see Table 1) and were instructed to respond to the rest of the items thinking about that main decision.

All participants completed surveys before viewing the decision aid including the SDM Process scale Pediatric version (scores range 0-4, higher scores indicate more SDM), decisional conflict, decision regret, and decision involvement. Participants in the intervention arm completed the knowledge survey after reviewing the decision aid.

Starting 7 days after they completed the survey, respondents were invited to complete a brief follow-up survey to examine short term test-retest reliability. The goal of the retest was to obtain 200 completed surveys. Consent was implied by completion of the survey.

Risks and Adverse Events: No diagnosis or treatments were offered or administered as part of this study. The standard of care is that physicians discuss appropriate treatment options, including their benefits and risks with the caregiver and child. There are minimal risks associated with participating in the online field. The respondents to the online panel have already given permission to be contacted by signing up for the panel. The participants in the online panel may stop their participation at any time. No confidential or PHI was collected as part of this study.

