- *Modified Control Preferences Scale (administered before the decision aid)*: 1-item, modified by the researchers and used in prior work,²⁰ asking who made the decision, with response options: “Mainly you”, “Mainly your child’s healthcare provider”, “You and the healthcare provider made the decision together”, and “Mainly someone else”.²¹ This version has not yet been used in a pediatric context, however the original Control Preference Scale been used in pediatric contexts.^{22,23}
- *Knowledge (administered after the decision aid)*: 7 multiple choice knowledge items that covered options, benefits and harms of medication and other treatments for ADHD. A total score (0-7) was created and converted to a 0-100% scale. Higher scores indicated higher knowledge.
- *ADHD severity* : Parent Informant Performance subscale of the National Institute for Children’s Health Quality (NICHQ) Vanderbilt Assessment Scales.²⁴ Score range from 8 to 40 with higher scores indicating more problematic behavior.

- *Demographic and other information:* Participants were also asked to report on demographic information, current ADHD treatment(s), prior AHDH treatment(s), and years with ADHD.

Sample Size: The sample size was determined to ensure sufficient power to detect differences in knowledge by DA exposure of about 0.25SD at 0.05 significance with 80% power would require 250 per group.

Statistical methods: First, we examined descriptive results for the main decision item, the SDM Process scale, knowledge and other outcomes.

For the SDM Process scale, we also looked to see whether the scores spanned the range of total possible scores, were normally distributed, and whether there was evidence of floor or ceiling effects. Using a one-way ANOVA we tested for differences in Pediatric SDM Process scores by main decisions.

Then we examined the convergent validity and reliability of the SDM Process scale. As there is no gold-standard for measuring SDM, we tested the following hypotheses to examine validity of the scales by looking at relationships between known constructs such as decision conflict and decision regret.

Validity Hypotheses

1. Patients with higher Pediatric SDM Process scores ($\geq .33SD$) were more likely to receive a top-score SURE score.
2. Patients with higher Pediatric SDM Process scores had less regret ($r \geq -.50$).

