3. Respondents who reported that their decision making process was mainly driven by the physician had lower Pediatric SDM Process scores ($\geq .33SD$) than respondents who reported that they were involved and engaged in selecting treatment.

For hypothesis 1, we compared mean Pediatric SDM Process scores for those who were SURE (score=4) and those who were not (score <4) with a Welch's 2-sample t-test since Pediatric SDM Process scores showed significant heterogeneity when examined for SURE groups. For hypothesis 2, we used a Pearson's correlation to determine the relationship between Pediatric SDM Process and regret. ANOVA determined if there were differences in Pediatric SDM Process scores by who made the decision.

We assessed retest reliability using Intraclass correlation coefficient (ICC; $ICC > 0.7$ indicating sufficient reliability).²⁵

We examined individual knowledge items for % correct and % missing data. We calculated a total knowledge score and looked to see whether the scores spanned the range of total possible scores, were normally distributed, and whether there was evidence of floor or ceiling effects. We ran r point-biserial correlations of individual items with the total knowledge score. We then compared knowledge scores between arms using two sample t-test.

Data Sharing: We are committed to making resources and data from the proposed research available to other investigators in the research community. The data collected in the online field test will be made available to others for analysis and research. The study team will create a complete, cleaned, de-identified copy of the final data set. Information for investigators interested in using this data will be made available on the Health Decision Sciences Center website and in publications of the data. [name] will share a de-identified data set with outside investigators at no cost, according to approved Mass General Brigham policies for data sharing. Investigators from other sites will be able to request the data and will be required to complete a data use agreement that ensures that all local IRB requirements are met before using the data, that they will not attempt to identify any data in the dataset, and that they will not share the data set with anyone outside their project team.

We will also make information necessary to interpret the data, such as study protocols, data dictionaries, and survey tools available to interested investigators.

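### Each knowledge item is correlated with a 7-item total that contains it, so the coefficients are inflated by overlap; item-rest correlations should be shown in place of them or beside them

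*Combined protocol and SAP*

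**What the plan says.** The Knowledge entry under Outcomes describes "7 multiple choice knowledge items that covered options, benefits and harms of medication and other treatments for ADHD". It then says: "A total score (0-7) was created and converted to a 0-100% scale". The total is therefore the sum of the seven items. The percentage scale is a linear rescaling and leaves any correlation with the total unchanged.

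The knowledge paragraph of Statistical methods starts with item description ("We examined individual knowledge items for % correct and % missing data"), looks at the distribution of the total, and continues: "We ran r point-biserial correlations of individual items with the total knowledge score". The next step is the comparison of the randomised arms: "We then compared knowledge scores between arms using two sample t-test".

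Nowhere does the document say that an item is taken out of the total before it is correlated with it. It gives no inter-item correlation, no percentage correct, no threshold for an acceptable item and no rule for dropping one.

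**The concern.** An item-level correlation in a test description is usually read as evidence of how well the item goes with the rest of the test. When the item is one of only seven components of the score, a good part of the coefficient is the item's correlation with itself. Three things follow for a reader of the item table.

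- The values look respectable even if the items share nothing.
- The self-contribution is larger for items with larger variance, that is, items near 50% correct. Part of any ranking of items then repeats the percentage correct, which is already reported.
- An item that runs weakly against the others, as a mis-keyed or misread item might, can still show a positive coefficient.

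What is at stake is the description of the instrument. The Purpose paragraph makes knowledge a secondary aim ("A secondary purpose is to evaluate the impact of a Decision Aid on participant knowledge of ADHD treatment options"), and no test or decision in the plan uses these coefficients.

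**Working it through.** **Inputs.** From the document: k = 7 items, a total that sums all seven, and "Participants were caregivers (n=498) of children (aged 5-13) diagnosed with ADHD". Assumed, because the document gives no values: the inter-item correlation r and the percentages correct. The plan reports no coefficient of its own on this point, so there is no figure to reproduce.

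**Equal item variances, common r.**

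- Item-total = (1 + 6r) / √(7 + 42r)
- Item-rest = 6r / √(6 + 30r)

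At r = .10: 1.6/√11.2 = 0.478, and 0.6/√9 = 0.200. A simulation of seven binary items at 60% correct gave the same two values.

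| Assumed r | Item-total | Item-rest | Gap |
|---|---|---|---|
| 0 | 0.378 | 0 | 0.378 |
| .10 | 0.478 | 0.200 | 0.278 |
| .20 | 0.561 | 0.346 | 0.214 |
| .30 | 0.632 | 0.465 | 0.168 |
| .50 | 0.756 | 0.655 | 0.101 |

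The gap shrinks as the items become more related, but its direction is the same throughout. For scale, the 95% margin on a correlation near zero is 1.96/√(498 − 3) = 0.088, if all 498 respondents are pooled with complete knowledge data.

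**Unequal difficulty, same phi for every pair.** Set C_ii = p_i·q_i and C_ij = r·√(p_i·q_i·p_j·q_j). Item-total is the row sum of C for the item, divided by √(C_ii × sum of C). Item-rest is the same with the item removed from the total. With assumed percentages correct of 90, 85, 80, 75, 70, 60 and 50:

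| Assumed r | Item-total, 90% item | Item-total, 50% item | Item-rest, all items |
|---|---|---|---|
| 0 | 0.267 | 0.445 | 0 |
| .10 | 0.399 | 0.526 | 0.198–0.199 |
| .20 | 0.500 | 0.597 | 0.344–0.346 |
| .30 | 0.585 | 0.661 | 0.463–0.464 |

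The near-constant last column is a product of assuming equal phi for all pairs.

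**Unequal difficulty, same latent (tetrachoric) correlation for every pair.** This drops the equal-phi assumption.

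| Assumed % correct | Latent correlation | Mean phi | Item-total | Item-rest |
|---|---|---|---|---|
| 90 to 50, as above | .20 | .106 | 0.38–0.54 | 0.18–0.23 |
| 95, 85, 70, 55, 40, 25, 10 | .40 | .18 | 0.36–0.64 | 0.23–0.39 |

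In the first row the spread falls from 0.16 to 0.05, in the second from 0.28 to 0.16. Item-rest values therefore depend on difficulty less, but still depend on it.

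**A hidden negative item.** Suppose equal variances, six items correlated .10 with each other, and a seventh correlated −.10 with each of them.

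- Item-rest for the seventh: 6 × (−.10)/√9 = −0.20.
- Item-total: covariance 1 − 0.6 = 0.4; total variance 9 + 1 − 1.2 = 8.8; 0.4/√8.8 = +0.13.

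The overlap reverses the sign.

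**The case against.** The strongest reply is that the plan does what it says. It names the total knowledge score as the comparator, an uncorrected item-total correlation is a recognised descriptive statistic, and the plan never presents it as the relation to the other six items. Nothing inferential hangs on it. The wording is also brief: a correction may have been applied without being mentioned, and the document cannot settle that. Most of this stands. It limits the point to a reporting improvement, but it does not remove it: with seven items the choice of version changes the number materially, and the text as written describes the uncorrected one.

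A second reply concerns comparability. A reader might infer that item-total values cannot be compared across items at all and that item-rest values would make them fully comparable. The calculations do not support that. Point-biserial coefficients depend on difficulty even after correction, as the equal-latent-correlation runs show, and in those runs the order of the items was nearly the same under both versions. Nor is the effect of difficulty always large against sampling error: at r = .30 under equal phi the item-total spread is 0.661 − 0.585 = 0.076, below the 0.088 margin. That margin is itself optimistic if data are missing or if the correlations were run by arm, which the plan does not say.

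Third, the sizes rest on assumed inter-item correlations and difficulties. That is so, which is why a range is shown; the gap is positive at every value tried.

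**Conclusion.** The point holds as a minor one, worth considering. As written, each of the seven coefficients is inflated by the item's overlap with itself. Under equal variances the excess is 0.38 for unrelated items, 0.28 at r = .10, 0.21 at r = .20 and 0.17 at r = .30. The excess varies with item difficulty and can hide a weak or negatively related item, so the values partly reflect percentage correct. Item-rest values lessen that dependence without removing it.

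A reader might go further and infer that the knowledge score or the decision-aid comparison is compromised. The document does not support that: the 0–7 total is defined independently of these correlations, and neither the sample size nor the t-test uses them. Nor is a low item-rest value by itself a reason to remove an item, since the questions cover separate facts about options, benefits and harms.

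**What to change.** Report the point-biserial correlation of each item with the sum of the other six, in place of the item-total value or in a column beside it, and label which version is shown. If the correction was already applied, the label alone settles the matter. It would help to add a line saying that item-rest values still depend to some degree on percentage correct.

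The cost is small. Data collection is over ("The online survey was fielded between February 2021 and March 2021") and the analyses are described in the past tense, so this is one re-run on existing data. If the item-total r, the percentage correct and the SD of the total are available for the same respondents, the item-rest value can be recovered exactly: (r·S_t − S_i)/√(S_t² + S_i² − 2·r·S_t·S_i), where r is the item-total correlation, S_t is the SD of the total on the 0–7 scale and S_i = √(p·q). The only downside is that the reported coefficients will be lower.

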There are no adverse events expected for this minimal risk survey study. Study staff will review the completed data set and will notify the site PI about any serious or moderate potential adverse events (AEs) immediately and any minor or potential ones at weekly meetings. The PI will review AEs individually real-time and in aggregate on a weekly, basis at team meetings. The PI and clinician co-investigators will review potentially serious adverse events (SAEs), as soon as

they are discovered. The PI ensures all protocol deviations, AEs, and SAEs are reported to the IRB according to the standard requirements.

There are no formal stopping rules for this minimal risk study.

Outcomes: The survey collected the following information:

- *SDM Process scale pediatric version (administered before the decision aid):* Four items cover discussion of options, pros, cons, and preferences.¹⁴ The items measures whether or not a specific behavior had occurred during an interaction with a healthcare provider about the treatment decision (see Table 2 for all items). Items were scored and summed in accordance with previously published work and a total score between 0 and 4 was calculated.¹⁴ Higher scores indicate more SDM occurred. Participants with missing answers were not given a Pediatric SDM Process score.
- *Decisional Conflict (administered before the decision aid):* The SURE scale is the 4-item short form of the Decisional Conflict Scale that measures the level of uncertainty about which treatment to choose. Each item is scored as “Yes” (1 point) or “No” (0 points) with total scores ranging from 0-4. A total score of 4 indicates no decisional conflict.^{15,16} SURE has been shown to correlate positively with the SDM Process score in a range of surgical decisions,¹⁴ as well as for decisions surrounding medication to manage depression.¹⁷ The longer Decisional Conflict scale has been used to measure decisional conflict both in surrogate decision makers,¹⁸ as well as in pediatric populations.¹⁹

- *Decision Regret (administered before the decision aid)*: 1 item assessed whether or not respondents would make the same decision again. Response options were on a scale from 1 (definitely make same decision again) to 4 (definitely NOT make same decision again). This item has not been used in pediatric studies, but has been used in previous studies by the authors and has been shown to be inversely related to the SDM Process scores for surgical decisions.¹⁴

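### Should the comparison of knowledge between arms have been adjusted for covariates rather than left as a plain t-test?

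*Combined protocol and SAP*

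**What the plan says.** The Design section sets the order of events: "After completing the main decision making surveys, participants in the sample will be randomized 1:1 to one of two arms". Survey protocol adds that "All participants completed surveys before viewing the decision aid including the SDM Process scale Pediatric version", and Outcomes places the conflict, regret and control-preference measures before the aid as well. Knowledge is taken after it. Knowledge is therefore the only outcome compared by arm, and Statistical methods gives that comparison one sentence: "We then compared knowledge scores between arms using two sample t-test". No covariate, stratification factor or adjusted model is named.

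Sample Size rests on the same contrast: "differences in knowledge by DA exposure of about 0.25SD at 0.05 significance with 80% power would require 250 per group". The Sample section gives the number obtained: "Participants were caregivers (n=498) of children (aged 5-13) diagnosed with ADHD". Purpose ranks the effect of the aid on knowledge as secondary; the primary purpose is the performance of the SDM Process scale.

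Other variables are on file. On the main decision, Survey protocol says: "They were asked to identify the main decision they made about ADHD medicine over the past two years". Under Outcomes: "Participants were also asked to report on demographic information, current ADHD treatment(s), prior AHDH treatment(s), and years with ADHD".

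**The concern.** Three features make the plain t-test look like a missed opportunity.

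- Knowledge is measured once, after the aid, so differences in what caregivers already knew stay in the error term.
- The survey holds variables that might absorb part of that variation: the main decision, the SDM Process score, current treatment and years with ADHD.
- Power at the planned difference is just under 80%, so there is no slack.

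If such variables predicted knowledge well, a small regression would give a narrower interval for the trial's only randomised contrast, using data already held. At stake would be precision only. Neither bias nor the type I error rate of the t-test is in question.

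**Working it through.** **Inputs.** From Sample Size: difference 0.25 SD, significance level 0.05, power 80%, 250 per group. From Design: 1:1 allocation. From Sample: 498 participants. Assumed, because not stated: a two-sided test, and 249 per arm. Also assumed: the share of knowledge variance explained by covariates, R², for which the documents give no figure.

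**1. The plan's own figure.** Normal approximation, per group:

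n = 2(1.960 + 0.842)² / 0.25² = 251.2, so 252.

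The noncentral t gives 253. Both agree with 250 to within about 1%. A one-sided test would need 198, which does not match, so two-sided is the natural reading.

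**2. The t-test as planned.** With n = 249 per arm and SD = 1:

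- standard error = √(2/249) = 0.0896
- 95% half-width = 1.965 × 0.0896 = 0.176 SD
- noncentrality = 0.25/0.0896 = 2.79 on 496 degrees of freedom, giving power 79.5%
- difference detectable with 80% power = 0.252 SD

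**3. A regression with k = 6 covariate degrees of freedom.** With N = 498:

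Variance = (2/249)(1 − R²)(N − 3)/(N − k − 3) = (2/249)(1 − R²)(495/489), on N − 2 − k = 490 degrees of freedom.

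The factor 495/489 = 1.012 is the expected price of chance imbalance in the covariates.

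| Assumed R² | Half-width (SD) | Change from t-test | Power at 0.25 SD |
|---|---|---|---|
| t-test | 0.1761 | – | 79.5% |
| 0% | 0.1772 | +0.6% | 79.0% |
| 2% | 0.1754 | −0.4% | 79.8% |
| 5% | 0.1727 | −1.9% | 81.0% |
| 10% | 0.1681 | −4.5% | 83.1% |
| 20% | 0.1585 | −10.0% | 87.2% |

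Without that price, and with normal quantiles, power is slightly higher (81.7% at R² = 5%, 83.7% at 10%). The picture is the same.

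**4. Break-even.** The regression beats the t-test only when R² exceeds 1.2% with 6 degrees of freedom, 3.0% with 15, or 5.1% with 25.

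**5. Missing covariates.** Outcomes states: "Participants with missing answers were not given a Pediatric SDM Process score". If 5% of participants dropped out of the regression for missing covariates, power at R² = 5% would be 79.0%, below the t-test, and break-even would rise to 6.2%. Avoiding this needs a rule for filling in covariates.

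**6. Which covariates.** The available text does not settle a set.

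- The response options for the main decision are in Table 1, which the text does not reproduce, so no grouping of them can be checked.
- Treatment and years with ADHD have no stated position relative to the aid.
- The measures confirmed as preceding the aid are the SDM Process scale, SURE, regret and control preferences. Nothing in the documents says how strongly any of them relates to knowledge.

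**7. Timing.** Fielding ran from February to March 2021. The document is dated August 10, 2023, and reports the comparison in the past tense. A covariate set chosen now would be post hoc unless the team could show it was fixed before knowledge was seen by arm.

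**The case for a change.** The strongest argument for adjusting is that the trade-off is lopsided. If six covariate degrees of freedom explain nothing, the extra model loses about 0.5 points of power and the t-test is untouched. If they explain 10%, its interval is 4.5% narrower; at 20%, 10% narrower. The data are already held, the contrast is the one used to size the study, and power sits at 79.5%.

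The arithmetic of this stands. A small model fixed before fielding would also have been a reasonable design choice.

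It does not make the plan deficient. As long as the t-test remains the main result, its interval and power do not change; any gain belongs to a second estimate of the same contrast. That estimate would probably carry a post hoc label, and readers would then have two answers to choose between. Power calculations also say little about a study whose data were collected in 2021. The gains worth having need an R² of 10% to 20%. Without a baseline knowledge score, the documents give no ground for expecting that.

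**Conclusion.** The concern does not hold. The t-test is a valid analysis of a 1:1 randomised comparison, and the stated sample size agrees with it. Leaving a secondary-purpose contrast unadjusted is a choice on which statisticians may differ, not an error.

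At R² of 2% to 5%, the half-width would shrink by 0.0007 to 0.0034 SD (from 0.1761 to 0.1754 and 0.1727), which is unlikely to alter a conclusion. At R² below 1.2% the adjusted interval would be slightly wider.

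These figures assume 249 per arm, a two-sided 0.05 test, a 0.25 SD difference, six covariate degrees of freedom and no participants lost to missing covariates. The judgement that there is no defect depends on none of the assumed R² values. It rests on the validity of the t-test under randomisation.
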